Clinical data from ISIS 505358-CS3 suggest that co-administration of GSK3228836 is unlikely to impact efficacy and safety profiles. Given the long plasma and tissue half-life of GSK3228836 (approximately 3 weeks), there is a period of at least several weeks during which there was a substantial presence of both drugs in the plasma, liver and other tissues. Potent reduction of HBV DNA was observed following initiation of tenofovir in all participants. There were no obvious differences in tenofovir potency and efficacy in participants who received 150 mg of GSK3228836 (Cohort 1), 300 mg of GSK3228836 (Cohorts 2 and 3), and placebo (no GSK3228836). There were no adverse event or clinical laboratory results that may indicate a change in tenofovir safety profile due to drug-drug interaction with GSK3228836.

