9.4.4. Secondary Endpoint(s)

9.4.4.1. Estimands for Secondary Objectives:

All analyses will be conducted separately for the 2 populations (on nucleos(t)ide treatment and not currently on nucleos(t)ide treatment).

Two groups of estimands are defined for the secondary efficacy objectives.

Categorical definitions for secondary analyses will be provided in the RAP.

Estimands supporting secondary objective of assessing the efficacy of GSK3228836 on biomarkers and virus-specific antibody responses are defined as follows:

- **Population**: one subpopulation of participants with CHB on stable nucleos(t)ide therapy and a second subpopulation of participants with CHB not currently on nucleos(t)ide therapy.
- Treatments: arms 1-4. Estimation within each arm.
- **Intercurrent events**: use of rescue medication, and discontinuation of/interruption of/adherence to IP. The use of rescue medication will be ignored (treatment policy strategy). Discontinuation of, interruption of, and adherence to IP will be ignored (treatment policy)

1) Categorical Variables:

- Achieving HBsAg <LLOQ and HBV DNA <LLOQ at the end of treatment.
- Categorical changes from baseline in HBsAg (e.g. $<0.5, \ge 0.5, \ge 1, \ge 1.5, \ge 3 \log_{10}$ IU/mL) and in HBV DNA (e.g. $<1, \ge 1, \ge 2, \ge 3 \log_{10}$ IU/mL). Additional categories of changes from baseline may be added in the RAP.
 - ALT normalization (ALT \leq ULN) over time in absence of rescue medication in participants with baseline ALT \rightarrow ULN
 - HBe antibody (anti-HBeAg) levels
- **Population summary:** proportion of participants in each category for each treatment arm.
- 2) Continuous Variables: Actual values and change from baseline over time of HBsAg and HBV DNA and actual values and change from baseline of HBeAg levels; HBs antibody (anti-HBsAg) levels.
- **Population summary**: mean values and mean changes from baseline for each variable in each treatment arm
- **3) Time to Event Variable**: Time to ALT normalization in absence of rescue medication in participants with baseline ALT>ULN

- **Population summary**: Turnbull's estimator for non-parametric estimation of Time to ALT normalization in each treatment arm

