4.3. Secondary Endpoint(s) Analyses

4.3.1. Key secondary endpoint(s)

4.3.1.1. Efficacy of GSK3228836 on biomarkers and virus-specific antibody response

The group of estimands supporting the secondary objective of assessing the efficacy of GSK3228836 on biomarkers and virus-specific antibody responses for each sub-population are the population summary for each variable in each treatment arm 1-4.

Missing data for variables defined above (except for Time to ALT normalization) will be ignored, only available data will be summarized. No sensitivity analysis is planned for the group of estimands supporting this objective.

Estimands supporting this objective are defined as follows:

- **Population**: one subpopulation of participants with CHB on stable nucleos(t)ide therapy and a second subpopulation of participants with CHB not currently on nucleos(t)ide therapy. For the time to ALT normalization endpoint, only subjects with ALT>ULN at baseline will be included. For summaries of HBe antibody (anti-HBeAg) levels, only participants who are HBeAg Positive at baseline will be included.
- Treatments: arms 1-4. Estimation within each arm.
- Intercurrent events: For the proportion of participants achieving HBsAg <LLOQ and HBV DNA <LLOQ in the absence of rescue medication at the end of treatment analysis window, end of treatment will be determined using the end of treatment analysis window defined in Section 4.2.2. In line with the primary endpoint, missing data not due to wide disruptive events will be imputed as non-response. Missing data due to wide disruptive events will be ignored without any imputation.

Other endpoints will be summarized regardless of completing IP, interruptions in IP or adherence to IP (treatment policy strategy) and regardless of rescue medication (except

for ALT normalization which can only be achieved in the absence of rescue medication). HBV DNA, HBsAg, HBeAg levels that are below the LLOQ will be imputed for summaries of actual values and change from baseline following the rules in Section 4.1.1.

1) Categorical Variables:

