- Achieving HBsAg <LLOQ and HBV DNA <LLOQ at the end of treatment analysis window. Data will be presented overall and by baseline stratification factors (HBsAg <3 log IU/mL and Negative HBeAg; BsAg >3 log IU/mL and Negative HBeAg; HBsAg <3 log IU/mL and Positive HBeAg; HBsAg >3 log IU/mL and Positive HBeAg; HBsAg <3 log IU/mL and All HBeAg; All HBsAg and Negative HBeAg; HBsAg <3 log IU/mL and All HBeAg; All HBsAg and Positive HBeAg)
- Categorical changes from baseline in HBsAg (e.g., <0.5, ≥0.5, ≥1, ≥1.5, ≥3 log₁₀ IU/mL) and in HBV DNA (e.g., <1, ≥1, ≥2, ≥3 log IU/mL). Change from baseline will be presented at each visit and for the following time periods: up to and including Week 6, Up to and including Week 12, Up to and including Week 24, Up to and including off-treatment Week 24. Data will be presented overall and by baseline stratification factors (HBsAg <3 log IU/mL and Negative HBeAg; BsAg >3 log IU/mL and Negative HBeAg; HBsAg >3 log IU/mL and Positive HBeAg; HBsAg >3 log IU/mL and All HBeAg; All HBsAg and Negative HBeAg; HBsAg <3 log IU/mL and All HBeAg; All HBsAg and Positive HBeAg)
- ALT normalization (ALT \leq ULN) over time in absence of rescue medication in participants with baseline ALT \rightarrow ULN
- HBe antibody (anti-HBeAg) levels in HBeAg Positive patients
- HBs antibody (anti-HBsAg) levels (HBs Antibody >=11.5 IU/L is HBs antibody positive and HBs Antibody <11.5 IU/L is HBs antibody negative)
- **Population summary:** proportion of participants in each category for each treatment arm.

2) Continuous Variables:

- Actual values and change from baseline over time of HBsAg and HBV DNA
- Actual values and change from baseline of HBeAg levels
- HBs antibody (anti-HBsAg) levels
- **Population summary**: mean values and mean changes from baseline for each variable in each treatment arm.

3) Time to Event Variable:

- Time to ALT normalization in absence of rescue medication in participants with baseline ALT>ULN.
- **Population summary**: Turnbull's estimator for the non-parametric estimation of time to ALT normalization in each treatment arm.

ALT normalization is defined in subjects with ALT>ULN at baseline as a return to ≤ULN (ULN = 40 for males and 33 in females). Time to ALT normalization is defined as time from baseline to the first follow-up where subject's ALT has returned to normal.

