4.4.3.1. HBV Genotype

HBV Genotype will be collected in the eCRF as well as identified by HBV Sequence. HBV Genotype from both data sources will be listed and the listing will include the final reported genotype.

For subjects with genotype both collected in the eCRF and determined by HBV Sequence the final reported genotype will be determined as follows:

For participants on stable nucleos(t)ide treatment:

• Genotype reported in the eCRF will take precedence

For participants currently not on nucleos(t)ide treatment:

- If the if the sequence genotype was derived from DNA, the HBV Sequence genotype will take precedence.
- If the if the sequence genotype was derived from RNA (i.e. rather than DNA due to low DNA levels hence RNA sequencing was employed), the genotype reported in the eCRF will take precedence similar to the participants on stable nucleos(t)ide.

Data from the Week 1 Day 1 visit will be used to determine HBV genotype by HBV DNA or RNA sequencing. However, as HBV genotype should not change over time, if a participant missed the Week 1 Day 1 visit, HBV genotype can be determined from a later sample if available.

The number of participants with each final reported genotype will be presented by arm and overall.

Baseline log HBsAg, change from baseline in log HBsAg at End of GSK836 Treatment visit (Week 12 / Week 24) and Off GSK836 Treatment Week 24 visit (Week 36 / Week 48), number of subjects achieving HBsAg < LLOQ at any time up to End of GSK836 Treatment visit (Week 12 / Week 24) or Off GSK836 Treatment Week 24 visit (Week 36 / Week 48), and mean time to achieving HBsAg < LLOQ will be presented for each arm separately. Results will be summarized by baseline final reported genotype.

For participants currently not on nucleos(t)ide treatment only, baseline log HBV DNA, change from baseline in log HBV DNA at End of GSK836 Treatment visit (Week 12 /

Week 24) and Off GSK836 Treatment Week 24 visit (Week 36 / Week 48), number of subjects achieving HBV DNA < LLOQ at any time up to End of GSK836 Treatment visit (Week 12 / Week 24) and Off GSK836 Treatment Week 24 visit (Week 36 / Week 48), and mean time to achieving HBV DNA < LLOQ will be presented for each arm separately. Results will be summarized by baseline final reported genotype.

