4.8. Changes to Protocol Defined Analyses

Changes from the originally planned statistical analysis specified in the protocol are detailed in Table 9.

Table 9 Changes to Protocol Defined Analysis Plan

Protocol Defined Analysis	SAP Defined Analysis	Rationale for Changes
NA - addition	SAP Section 4.2.4.3: Addition of a supplementary estimand that uses a principal stratum strategy to deal with protocol deviations	A number of subjects in the not currently on nucleos(t)ide therapy population started nucleos(t)ide therapy on day 1 because of a misunderstanding of the protocol. In the main estimand these participants will be treated as failures on day 1. However, as these patients never had the chance to respond because of an

Protocol Defined Analysis	SAP Defined Analysis	Rationale for Changes
		operational error, this estimand will be used to counter the main estimand,
NA - addition	SAP Section 4.2.4.4: Addition of a supplementary estimand to assess efficacy using a modified definition of SVR	There are a number of subjects with single lab values that are aberrant in terms of the individual's overall trajectory of response. There is some evidence that the aberrant values have occurred because of an unresolvable error at the site/lab. As the issues cannot be resolved in the data, this estimand will be used to support the primary objective.

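### In the not-on-NA cohort, HBV DNA change summaries keep values after rescue nucleos(t)ide under an objective worded as efficacy of GSK3228836, with no supporting analysis

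*SAP*

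**What the plan says.** SAP 4.3.1.1 serves the secondary objective of "assessing the efficacy of GSK3228836 on biomarkers and virus-specific antibody responses". Its HBV DNA endpoints are log-decline categories, at each visit and cumulatively up to off-treatment Week 24, and, among the continuous variables, "Actual values and change from baseline over time of HBsAg and HBV DNA". For these the rule is "Other endpoints will be summarized regardless of completing IP, interruptions in IP or adherence to IP (treatment policy strategy) and regardless of rescue medication". The same section adds: "No sensitivity analysis is planned for the group of estimands supporting this objective". Protocol 9.4.4.1 agrees: "The use of rescue medication will be ignored (treatment policy strategy".

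Rescue is defined in Protocol 9.1 and SAP 2 as any medication started for antiviral suppression. On what NA does to this variable, Protocol 4.3 reports: "Potent reduction of HBV DNA was observed following initiation of tenofovir in all participants".

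In the not-on-NA cohort, Protocol 6.5.2 asks investigators to consider NA for virological breakthrough, no response (less than 1 log HBV DNA decline by Week 12) or partial response. Section 6.5.3 leaves NA after treatment to their discretion, and 6.5.1 and 7.1.1 add an ALT-plus-bilirubin rule. SAP Table 9 records that some participants in this cohort "started nucleos(t)ide therapy on day 1 because of a misunderstanding of the protocol".

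SAP 4.4.3.1 summarizes HBV DNA change, the "number of subjects achieving HBV DNA < LLOQ at any time" and the mean time to reach <LLOQ by genotype. SAP 4.4.3.2 repeats this by baseline binding-site polymorphism. Neither states a rescue rule for these summaries.

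**The concern.** The objective attributes the result to GSK3228836, but the retained values also contain the effect of a second antiviral acting on the same variable. One of its triggers is the endpoint's own lowest category: a participant with less than 1 log decline by Week 12 may be given NA and can later be counted at ≥1, ≥2 or ≥3 log. For Day 1 error starters, the whole on-study HBV DNA course is under NA. SAP 4.2.4.3 handles them by a separate estimand for SVR, but nothing comparable exists here.

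At stake is how the HBV DNA tables by arm, genotype and polymorphism are read in this cohort. A fall in them cannot be assigned to GSK3228836 without knowing how much of it followed rescue, and differences between arms may be distorted if rescue use differs.

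**Working it through.** **Which outputs are exposed.** The plan gives no rescue rate, NA effect size or expected HBV DNA change for these endpoints, so there is no figure to reproduce. The rules side by side:

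| Output | Rescue rule | Place |
|---|---|---|
| SVR | rescue makes a non-responder | SAP 4.2.2.2 |
| HBsAg and HBV DNA <LLOQ at end of treatment | absence of rescue required | SAP 4.3.1.1 |
| ALT normalization | not achievable after rescue | SAP 4.3.1.1 |
| Mutation-by-response 2x2 tables | no rescue, or SVR | SAP 4.4.3.2 |
| HBV DNA actual values, change, log-decline categories | rescue ignored | SAP 4.3.1.1 |
| HBV DNA change, <LLOQ at any time, time to <LLOQ | none stated | SAP 4.4.3.1, 4.4.3.2 |

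Only the last two rows are exposed.

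**Illustration of size.** All inputs here are assumptions:
- f = share failing virologically: 40% in Arm A, 80% in Arm B (hypothetical arms)
- u = NA uptake among failures: 25% to 75%
- R = −3 and F = −0.5 log10, the change in responders and in failures without NA
- D = −3 to −5 log10, the change after NA

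Mean without credit for NA: (1−f)R + fF. Arm A: 0.6×(−3) + 0.4×(−0.5) = −2.0. Arm B: 0.2×(−3) + 0.8×(−0.5) = −1.0.

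Mean under treatment policy: (1−f)R + f[(1−u)F + uD]. The shift is f×u×(D−F).

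| Case | Arm A | Arm B | B minus A |
|---|---|---|---|
| No NA credit | −2.0 | −1.0 | 1.0 |
| u 25%, D −3 | −2.25 | −1.5 | 0.75 |
| u 50%, D −4 | −2.7 | −2.4 | 0.3 |
| u 75%, D −5 | −3.35 | −3.7 | −0.35 |
| u 75% in A and 25% in B, D −4 | −3.05 | −1.7 | 1.35 |

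Across the equal-uptake cases the shift is 0.25 to 1.35 log in Arm A and 0.5 to 2.7 log in Arm B, and the gap shrinks or reverses. In the last row uptake differs and the gap widens: A shifts by 0.4×0.75×3.5 = 1.05 and B by 0.8×0.25×3.5 = 0.7. So even the direction of the distortion between arms depends on uptake.

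**Ceiling.** Entry requires HBV DNA >2000 IU/mL (Protocol 5.1), and SAP 4.1.1 imputes target-not-detected as 1 IU/mL. Near the entry limit the largest fall is about log10(2000) = 3.3. D = −4 or −5 needs a baseline of at least 10^4 or 10^5 IU/mL.

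**Proportion with ≥3 log decline.** Assume it is reached by 50% of responders, no unrescued failures, and w = 50% to 90% of rescued participants. The proportion is (1−f)×0.5 + f×u×w. Arm A: 30% without NA credit, 35% to 57% with it. Arm B: 10% without, 20% to 64% with.

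**Day 1 error starters.** Their number is not given. With k among 66 in an arm and an assumed change of −1.5 log had they not taken NA, the mean shifts by k/66×(D+1.5). For k = 1 and D = −3 this is 0.02 log in size; for k = 5 and D = −5 it is 0.27 log.

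**The case against.** The strongest defence is that treatment policy is a declared estimand, stated consistently in the protocol and the SAP with ALT normalization as a named exception. It validly describes GSK3228836 plus whatever NA follows. The summaries are descriptive, within arm, and no decision rule in the protocol or SAP uses HBV DNA change: arm comparisons and regimen selection rest on SVR. SAP 6.1.2 also presents NA started after randomization. All of this stands. It means the treatment-policy tables should be kept, and the gap is the absence of any companion analysis that matches the objective's wording. A separate NA-use table discloses rescue but does not show how much of an HBV DNA result depends on it.

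A second fair objection is that simply dropping post-rescue values is also biased. Rescue is partly triggered by poor response, so the remaining values favour responders. This stands too and shapes the remedy.

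A reader might infer that the distortion is largest in the arms that fail most. The documents do not support this as fact. NA start for virologic reasons is discretionary. The ALT-plus-bilirubin rule and the Day 1 errors are not virologic failure, and Protocol Table 5 reports earlier ALT elevations alongside HBsAg reductions, so rescued participants may include responders. Protocol 6.5.2 withholds NA in Arm 4 during its 12 placebo weeks.

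A reader might also infer that Arm 3, which stops active drug at Week 12, has longer to be rescued. In the by-visit tables every arm has the same time since baseline. In the virology change summaries Arm 3 is read at Weeks 12 and 36, against Weeks 24 and 48 for Arms 1 and 2, which gives it less calendar time.

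**Conclusion.** The concern holds in limited form. In the not-on-NA cohort, the HBV DNA change endpoints in SAP 4.3.1.1 and the HBV DNA summaries in 4.4.3.1 and 4.4.3.2 count values after rescue NA, including those of Day 1 error starters, and nothing planned separates the two drugs. NA-driven falls therefore enter summaries labelled as efficacy of GSK3228836, and comparisons between arms may be distorted if rescue use differs.

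The size and the direction by arm cannot be derived from the documents. The 0.25 to 2.7 log range rests wholly on the assumed f, u, R, F and D, and its upper end needs high baseline HBV DNA.

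It would be wrong to read this as affecting every endpoint that contains HBV DNA: SVR, the end-of-treatment composite, the mutation-by-response tables and regimen selection already exclude rescue. Because the exposed endpoints are descriptive and feed no planned decision, this is a low-cost improvement rather than a must-fix.

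**What to change.** Keep the treatment-policy summaries. For the not-on-NA cohort, add to SAP 4.3.1.1:

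- **(a) A composite version.** Only values before rescue start can count towards ≥1, ≥2 or ≥3 log decline or HBV DNA <LLOQ. A participant who has not met the category by then is a non-achiever from that point. A decline reached before rescue still counts in the cumulative periods.
- **(b) Rescue counts.** Show the number rescued, by arm and visit, beside each HBV DNA table, with Day 1 error starters shown separately.
- **(c) Supplementary only.** Give continuous summaries with post-rescue values excluded, labelled as favouring responders because poor response partly triggers rescue.

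Apply (a) and (b) to the HBV DNA summaries in SAP 4.4.3.1 and 4.4.3.2. Align the estimand text in Protocol 9.4.4.1 and SAP 1.1. Both still except only ALT normalization from the rule of ignoring rescue, whereas SAP 4.3.1.1 already requires absence of rescue for the end-of-treatment composite.

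The cost is SAP wording and a few extra tables. Medication start dates are already recorded under Protocol 6.5, so no new data are needed.

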8.1. Efficacy Assessments

The primary objective measurements for efficacy include:

- HBsAg
- HBV DNA

HBsAg and HBV DNA are collected as per the SoA. Details of sample collection can be found in the SRM.

The primary efficacy endpoint is sustained virologic response, which is a composite endpoint defined as HBsAg <LLOQ and HBV DNA <LLOQ at the end of GSK3228836 treatment which is sustained for 24 weeks post-GSK3228836 treatment. Seroclearance refers to participants with HBsAg and HBV DNA <LLOQ (with or without the formation of HBs-antibody). Seroconversion refers to participants with HBsAg and HBV DNA <LLOQ plus formation of HBs-antibody. Both terms are used to evaluate efficacy. For the purposes of this study, sustained response is defined as a continuous 24 weeks from end of GSK3228836 treatment during which levels of HBsAg in serum remain less than LLOQ and HBV DNA less than LLOQ.

Any HBsAg greater than LLOQ or HBV DNA greater than LLOQ after achieving HBsAg seroclearance and HBV DNA suppression needs to be confirmed by re-test within 1 week of receiving the test result. The re-test result will be used if the first test is not confirmed.

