4.6.7. Other variables and/or parameters

Fibrosis Score is collected at baseline and End of Study (or Early Termination). A shift table for Metavir fibrosis score showing baseline score and End of Study (or Early Termination) score will be provided for each arm, overall and by baseline HBeAg status.

A listing of participants who went above and stayed above >=90 IU/mL HBV DNA will be presented. All visits will be presented for these participants.

A listing showing (quantitative) values of HBeAg at Baseline & Day 1 will be presented for subjects who are anti-HBeAg positive at baseline. A listing showing (quantitative) values of HBsAg at Baseline & Day 1 will be presented for subjects who are anti-HBsAg positive (i.e. HBs Antibody >=11.5 IU/L) at baseline.

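### The SAP's anti-HBs and anti-HBe category summaries do not separate new antibody from antibody already present at baseline, and do not yield the seroconversion term defined in Protocol 8.1

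*SAP*

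**What the plan says.** The secondary objective in SAP 4.3.1.1 concerns the effect of GSK3228836 on biomarkers and on virus-specific antibody responses. Its antibody variables are as follows.

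- Anti-HBs, categorical: "HBs antibody (anti-HBsAg) levels (HBs Antibody >=11.5 IU/L is HBs antibody positive and HBs Antibody <11.5 IU/L is HBs antibody negative".
- Anti-HBe, categorical: "HBe antibody (anti-HBeAg) levels in HBeAg Positive patients". The population paragraph of the same section repeats the restriction: "For summaries of HBe antibody (anti-HBeAg) levels, only participants who are HBeAg Positive at baseline will be included". No cut-off or category is given for anti-HBe.
- Summary for the categorical variables: "proportion of participants in each category for each treatment arm".
- Anti-HBs is also a continuous variable, summarised as "mean values and mean changes from baseline for each variable in each treatment arm".

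Protocol 8.1 defines a stricter term, "Seroconversion refers to participants with HBsAg and HBV DNA <LLOQ plus formation of HBs-antibody", and states that seroclearance and seroconversion both serve to evaluate efficacy. Protocol 9.4.4.1 leaves the categorical definitions for secondary analyses to the analysis plan.

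SAP 4.6.7 plans a listing in which "values of HBsAg at Baseline & Day 1 will be presented for subjects who are anti-HBsAg positive" at baseline, and a parallel listing of HBeAg values for those anti-HBe positive at baseline.

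**The concern.** The objective is worded as antibody response, and the protocol's term speaks of antibody being formed. A proportion above a cut describes status. A participant who was above 11.5 IU/L before the first dose and stays there counts the same as one who crossed the cut on treatment with HBsAg cleared.

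Such participants can enter the trial. The screening hepatitis B profile in the Schedule of Activities is HBsAg, HBV DNA and HBeAg, without either antibody, and no criterion in Protocol 5.1 or 5.2 excludes antibody positivity. Entry requires HBsAg above 100 IU/mL, so a participant anti-HBs positive at entry has not seroconverted in the protocol's sense. The listings in SAP 4.6.7 show that the plan foresees these participants.

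At stake is whether a descriptive secondary result can be read as antibody induced by treatment. As written, a reader of the clinical study report could not tell from the proportion alone.

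**Working it through.** **Comparing the definitions**

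| Condition | Protocol 8.1, HBs seroconversion | SAP 4.3.1.1, anti-HBs category | SAP 4.3.1.1, anti-HBe summary |
|---|---|---|---|
| Antibody new since baseline | Yes (formation of antibody) | Not required | Not required |
| Matching antigen lost | HBsAg <LLOQ | Not required | HBeAg loss not required |
| HBV DNA <LLOQ | Yes | Not required | Not required |
| Restriction by baseline antigen | All enter HBsAg positive | None | HBeAg positive at baseline |

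The anti-HBe restriction narrows the problem: pre-existing antibody can enter that summary only through participants positive for both HBeAg and anti-HBe at baseline.

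The SAP ties other variables to baseline. ALT normalisation requires baseline ALT above ULN (4.3.1.1), HBsAg and HBV DNA categories are changes from baseline (4.3.1.1), treatment-emergent mutations require a frequency below 5% at baseline (4.4.3.2), and ANCA is shown as shifts from baseline (4.5.3.1).

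**Weight of one participant**

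The plan states no expected rate or precision for the antibody variables, so there is no figure to reproduce. Arm sizes per population are 66 (Arms 1 to 3) and 22 (Arm 4), from SAP 5.

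- Anti-HBs, Arms 1 to 3: 1/66 = 1.5 points.
- Anti-HBs, Arm 4: 1/22 = 4.5 points.
- Anti-HBe: the denominator is the HBeAg-positive subset, whose size is not given. It cannot exceed the arm, so one participant weighs at least these amounts.

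**Illustration**

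Let b be the share anti-HBs positive at baseline and c the rate of new positivity among baseline negatives. If baseline positives stay positive:

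crude proportion positive = b + (1 − b) × c; share of positives that is pre-existing = b / crude.

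Neither b nor c is in the documents. With c assumed at 5%:

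- b = 0%: crude 5.0%, pre-existing share 0%.
- b = 2%: 0.02 + 0.98 × 0.05 = 6.9%; 0.02/0.069 = 29%.
- b = 5%: 0.05 + 0.95 × 0.05 = 9.8%; 0.05/0.0975 = 51%.
- b = 10%: 0.10 + 0.90 × 0.05 = 14.5%; 0.10/0.145 = 69%.

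With c = 0% the crude proportion equals b, whatever the treatment does. Restricting the denominator to baseline negatives returns c in every case.

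**Can the stricter variables be derived?**

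Both antibodies are scheduled at Day 1, Day 29, Days 57, 85, 113 and 141, and every off-treatment visit. HBsAg and HBV DNA are scheduled at all those visits, and so is HBeAg for participants HBeAg positive at screening. Anti-HBs is not drawn at the Week 12 or Week 24 visit itself, but every primary-endpoint window contains a scheduled sample. For example, off-treatment Day 1 (Day 169) lies in the end-of-treatment window for Arms 1, 2 and 4 (Days 148 to 182), and Day 85 lies in that for Arm 3 (Days 64 to 98).

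**The case against.** The strongest reply is that the SAP never claims to report response. It reports antibody levels in two categories, sets no responder rule and names no timepoint for them. A reader might infer that anyone antibody positive after baseline will be reported as a responder. The documents do not support that: the word response appears only in the objective, and baseline HBeAg-negative participants are outside the anti-HBe summary. This stands, and the point is limited accordingly.

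Second, seroconversion is not among the protocol's secondary estimand variables, which are antibody levels. Protocol 8.6 lists it as a pharmacodynamic parameter, and the PK-PD and biomarker plans are separate documents not available here. So it cannot be said that seroconversion goes unanalysed. It can be said that the section carrying the antibody objective does not define it, although Protocol 9.4.4.1 leaves categorical definitions to the analysis plan.

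Third, baseline status is partly visible through the mean change in anti-HBs and the SAP 4.6.7 listings. This helps only in part. A mean does not show who converted, anti-HBe has no continuous summary, and the listings give antigen values at baseline and Day 1 without removing anyone from the proportions.

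Fourth, baseline anti-HBs may be uncommon. Protocol 2.2 says the antibody is detectable only in immune complexes because antigen is in excess, and entry requires HBsAg above 100 IU/mL. This is fair, and it means the effect could be negligible. The same passage suggests, as an inference, that lowering HBsAg without clearing it might expose existing antibody; the antigen condition guards against that, whereas a negative-baseline condition alone would not.

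Fifth, a reader might infer that chance imbalance in baseline positives could be mistaken for a regimen difference. The plan specifies estimation within each arm for this objective, and its arm comparisons and regimen selection (SAP 4.3.1.2) use SVR only.

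**Conclusion.** The concern holds in a limited form. The categorical antibody summaries in SAP 4.3.1.1 cannot distinguish new from pre-existing antibody and do not produce the seroconversion term of Protocol 8.1.

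The size cannot be determined from the documents. The weight per baseline-positive participant is fixed by arm size. The 29% to 69% pre-existing share for b of 2% to 10% follows from assumed inputs, including persistence of baseline positivity, and is not an estimate for this trial. A reader might conclude that half or more of the reported positives would be pre-existing; no prevalence in the documents supports that.

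The consequence is confined to descriptive secondary results. SVR is built from HBsAg, HBV DNA and rescue medication, so the primary endpoint is untouched. This is a worthwhile, low-cost improvement in derivation, not a threat to the trial's main conclusions.

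**What to change.** In SAP 4.3.1.1 add two derived variables.

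- **HBs seroconversion:** anti-HBs below 11.5 IU/L at baseline, then at or above 11.5 IU/L with HBsAg and HBV DNA both <LLOQ in the same analysis window, following Protocol 8.1.
- **HBe seroconversion:** HBeAg positive and anti-HBe negative at baseline, then HBeAg negative and anti-HBe positive. State the anti-HBe positivity rule, which the SAP does not give.

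Use baseline antibody negatives as the denominator, show baseline-antibody-positive participants in a separate row, and name the windows reported. Keep the existing category and level summaries. If seroconversion is already derived in a separate plan, cross-refer to it and use one definition.

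The cost is SAP wording and programming; no new samples are needed. The denominators become slightly smaller and the reported proportion may be less favourable.
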